To evaluate the efficacy of tralokinumab in combination with TCS on patient-reported outcomes compared to placebo in combination with TCS.	
 • Change from baseline to Week 16 in SF-36 score • Change from baseline to Week 26 in SF-36 score • Change from baseline to Week 16 in POEM • Change from baseline to Week 26 in POEM • Reduction from baseline to Week 16 of POEM of ≥ 4 points among subjects with baseline POEM ≥ 4 • Reduction from baseline to Week 26 of POEM of ≥ 4 points among subjects with baseline POEM ≥ 4 • Change from baseline to Week 16 in EQ-5D-5L score • Change from baseline to Week 26 in EQ-5D-5L score • Change from baseline to Week 16 in EQ-5D-5L VAS score • Change from baseline to Week 26 in EQ-5D-5L VAS score • Change from baseline to Week 16 in HADS • Change from baseline to Week 26 in HADS • HADS-anxiety and HADS-depression scores < 8 at Week 16 • HADS-anxiety and HADS-depression scores < 8 at Week 26 • Change from baseline to Week 16 in HADS-anxiety score • Change from baseline to Week 26 in HADS-anxiety score • Change from baseline to Week 16 in HADS-depression score • Change from baseline to Week 26 in HADS-depression score
To evaluate the efficacy of tralokinumab in combination with TCS on health care resource utilisation compared to placebo with TCS.	
 • Amount of TCS used from baseline to Week 16 • Amount of TCS used from baseline to Week 26 • Number of days without topical treatment use from baseline to Week 16 • Number of days without topical treatment use from baseline to Week 26

Abbreviations: AD, atopic dermatitis; ADA, anti-drug antibodies; CSA, cyclosporine A; DLQI, Dermatology Life Quality Index; EASI, Eczema Area and Severity Index; EASI75/90, at least 75/90% reduction in EASI score; EQ-5D-5L, EuroQoL 5-Dimension Health Questionnaire 5 Level; HADS, Hospital Anxiety and Depression Scale IGA, Investigator's Global Assessment; NRS, numeric rating scale; POEM, Patient-Oriented Eczema Measure; SCORAD, Scoring Atopic Dermatitis; SF-36: Short Form-36 questionnaire; TCS, topical corticosteroids.

7 Trial design

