9.5 Rescue treatment

If medically necessary (i.e., to control intolerable AD symptoms), rescue treatment for AD may be provided to trial subjects at the discretion of the investigator. If possible, investigators should attempt to limit the first step of rescue therapy to topical medications (i.e. higher potency TCS, Europe class >3), and escalate to systemic medications only for subjects who do not respond adequately after at least 14 days of topical treatment. The subject will be monitored for signs of local or systemic TCS toxicity and the safety and appropriateness of continued use will be supervised by site staff.

Subjects who receive topical rescue treatment (higher potency TCS, Europe class >3) will continue IMP treatment.

If a subject receives rescue treatment with systemic corticosteroids or non-steroidal systemic immunosuppressive drugs (methotrexate, mycophenolate mofetil, azathioprine, etc.), IMP will be immediately discontinued (see Section 10.2.2). After the treatment with these medications is completed, IMP may be resumed if deemed appropriate by the investigator, but not sooner than 5 half-lives after the last dose of systemic rescue treatment. The use of biological rescue treatment will be disallowed for the entire trial duration.

Investigators should make every attempt to conduct efficacy and safety assessments (at least disease severity scores [IGA and EASI], concomitant medications/ procedures, and AEs) immediately before administering any rescue treatment. An unscheduled visit may be used for this purpose, if necessary. In the primary efficacy analyses, subjects who receive higher potency TCS (Europe Class >3) or systemic rescue treatment during the treatment period will be considered as non-responders.

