11.3.4.3 Patient Days of Topical Treatment Use

Subjects will assess their use of topical AD treatment over the past 24 hours using a response scale (‘yes’, ‘no’). Subjects will complete the Patient Days of Topical Treatment Use as part of an eDiary each day in the morning from baseline (Week 0 [visit 3]) until Week 26.

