14.3.10 Analysis of other endpoints

All binary endpoints listed under ‘Other endpoints’ (Panel 4) will be analysed as for the primary analysis of the primary and secondary estimands for the primary endpoint and presented for the FAS at Week 16 and Week 26.

All continuous endpoints listed under ‘Other endpoints’ (Panel 4) will be analysed as for the primary analysis of the primary and secondary estimands for the continuous secondary endpoints. For the Eczema-related Sleep NRS score, the mean over the last 7 days prior to randomisation will be used as the baseline value. For the Worst Daily Pruritus NRS and Eczema-related Sleep NRS scores, it is expected that subjects will return their eDiaries upon permanent discontinuation of IMP, and no data is available after that point. Thus, analysis

using the primary analysis of the secondary continuous estimand will not be possible in the ‘Other endpoints’ with Worst Daily Pruritus NRS or Eczema-related Sleep NRS scores.

To evaluate the efficacy related to health care resource utilisation, the amount of TCS used (assessed as the amount of TCS used between visits) will be determined over 2-week periods, and the number of days without topical treatment use (collected as Patient Days of Topical Treatment Use in the eDiary) will be determined over 1-week periods. The amount of TCS used and the number of days without topical treatment use will each be analysed using a repeated measurements model with an unstructured covariance matrix and the mean modelled as follows:

$$Y = \text{treatment} \times [\text{visit/week}] + \text{prior CSA use} + \text{country} + \text{baseline IGA}$$

where ‘Y’ is either the amount of TCS used or the number of days without topical treatment use. Data obtained after permanent discontinuation of IMP, after initiation of rescue treatment, or after subject-onset of the COVID-19 pandemic will be excluded from the analyses.

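### The only model specified for days without topical treatment drops diary data after rescue, so it estimates use in a world without rescue, not the topical use of the two regimens

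*Protocol*

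**What the plan says.** Panel 4 (Protocol Section 6) states the objective: "To evaluate the efficacy of tralokinumab in combination with TCS on health care resource utilisation compared to placebo with TCS". Its endpoints are the amount of TCS used and the number of days without topical treatment, each from baseline to Week 16 and to Week 26. Neither is limited to the time before rescue.

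Section 14.3.10 says that the two outcomes "will each be analysed using a repeated measurements model with an unstructured covariance matrix", with treatment by visit or week, prior CSA use, country and baseline IGA in the mean. Besides data after permanent IMP discontinuation, data "after initiation of rescue treatment, or after subject-onset of the COVID-19 pandemic will be excluded from the analyses".

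Section 9.5 says that, if possible, "investigators should attempt to limit the first step of rescue therapy to topical medications", and then: "Subjects who receive topical rescue treatment (higher potency TCS, Europe class >3) will continue IMP treatment". Section 11.3.4.3 defines the diary item: "Subjects will assess their use of topical AD treatment over the past 24 hours", answered yes or no. Panel 2 has it completed daily from Week 0 to Week 26.

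SAP Section 6.6.5 keeps the protocol method for both endpoints. Its sensitivity analyses concern grams of TCS only, and vary only the handling of unreturned tubes and the scale (log or original).

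**The concern.** For SCORAD or DLQI, rescue is an outside event that disturbs the outcome. For days without topical treatment, topical rescue is itself a use of the resource being counted. Counting stops when it starts, although the subject stays on IMP and continues the diary. A likelihood-based repeated measurements model then treats the later weeks as missing at random, so in effect they follow the subject's pre-rescue course.

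At stake is what the reported difference means. A reader of a resource-use result will take it as the topical treatment that each regimen entails over 16 or 26 weeks. The specified model gives the use that would have been seen had no one been rescued. No other between-group estimate is spelled out for this endpoint.

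**Working it through.** **Plan's own figures.** The documents give no rescue rate, usage level or power for the resource-use endpoints. The stated power concerns other endpoints and does reproduce: for EASI75, 125 per arm at 40% against 15% gives 99.5% (stated 99%). For itch, 30% against 15% gives 81.4%, or 81.0% jointly with EASI75 if the two are independent (stated at least 80%). Nothing below depends on these.

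**Passages side by side.**

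| Question | Source | Answer |
|---|---|---|
| Period of the endpoint | Panel 4 | Baseline to Week 16 / 26, no pre-rescue limit |
| Data in the model | Protocol 14.3.10 | None after rescue |
| First rescue step | Protocol 9.5 | Topical, if possible |
| IMP after topical rescue | Protocol 9.5 | Continues |
| Diary after topical rescue | Panel 2, footnote 6 | Daily to Week 26 |
| What the diary counts | Protocol 11.3.4.3 | Any topical AD treatment |
| Diary after IMP discontinuation | Panel 3, footnote 5 | Daily to the nominal Week 26 visit |
| Same question | Protocol 14.3.10 (pruritus and sleep NRS, same eDiary) | eDiary expected back; no later data |
| Treatment policy for continuous 'Other' endpoints | Protocol 14.3.10, opening rule | Yes, for all |
| Treatment policy for these two endpoints | Protocol 14.3.10, specific paragraph | Not described |

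SAP Section 6.8.6 counts an event as prior if it precedes the visit date. The interval in which rescue starts is then also dropped if rescue precedes the visit that closes it.

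**What the exclusion does to the estimate.** Let r be the share of an arm rescued by a given week. Let d be actual use after rescue minus the use that the model implies. Using post-rescue data moves the difference (tralokinumab minus placebo) by

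shift = r_T × d_T − r_P × d_P, which is (r_T − r_P) × d when d is the same in both arms.

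All inputs here are assumptions. For days without topical treatment per week, with rescued subjects losing 1, 2 or 4 such days (d = −1, −2, −4):

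| Rescued, T vs P | r_T − r_P | d = −1 | d = −2 | d = −4 |
|---|---|---|---|---|
| 3% vs 10% | −0.07 | +0.07 | +0.14 | +0.28 |
| 5% vs 20% | −0.15 | +0.15 | +0.30 | +0.60 |
| 10% vs 30% | −0.20 | +0.20 | +0.40 | +0.80 |
| 10% vs 10% | 0 | 0 | 0 | 0 |

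The sign is not fixed. At 10% in both arms, with losses of 2 days on tralokinumab and 1 on placebo, the shift is 0.10 × (−2) − 0.10 × (−1) = −0.10. If rescue lowered topical use (d = +1) at 5% against 20%, it is (−0.15) × 1 = −0.15.

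**Simulation of the mechanism.** 200 runs, 125 per arm, 8 two-week intervals, means 70 against 100 g, heavier users more likely to be rescued, about 2% against 8% rescued by the last visit. Grams serve here only as a convenient continuous outcome.

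| Change after rescue | Pre-rescue data only | All data |
|---|---|---|
| −60 g | −29.0 | −26.3 |
| 0 | −28.7 | −29.7 |
| +60 g | −29.4 | −34.2 |

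The analysis of pre-rescue data stays near −29 g whatever follows rescue; the all-data difference moves with it. The gap of 1.0 g in the middle row arises because rescue was made to depend on use in the very interval that is then dropped.

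**The case against.** Several points on the other side stand.

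- **A treatment-policy analysis may have been intended.** The opening rule of Section 14.3.10 gives every continuous 'Other' endpoint in Panel 4 hypothetical and treatment-policy analyses, and says treatment policy is not possible only for the pruritus and sleep NRS. SAP Section 6.6.5 also moves 'Other' endpoints to treatment policy, although its numbering of the estimands is that of the binary endpoints. The specific paragraph describes only the exclusion model, so the plan is unclear.
- **The no-rescue question is legitimate.** It matches the primary estimand for the continuous secondary endpoints. Rescue is also tabulated by type and shown in Kaplan-Meier plots (Protocol 14.3.5), and observed scores are summarised by visit (SAP 6.6.9). A reader might infer that the plan leaves the resource objective wholly unanswered; that goes too far. But none of these is a between-group estimate of topical use regardless of rescue.
- **A reader might infer that the heaviest users are removed.** Pre-rescue data stay in, so subjects are censored at rescue, and the documents give no usage by rescue status. Rescue is defined by drug class, agent or investigator confirmation, not by diary days.
- **A reader might infer that treatment-free days are overstated in both arms, or that a particular arm is favoured.** A subject already using TCS daily who moves to a stronger product shows no change on a yes/no item, and some rescue will be systemic and might reduce topical use.
- **A reader might extend the point to grams.** Section 9.2.2 describes weighing of supplied tubes only and says lower-potency products are not weighed; no weighing of rescue TCS is described. Supplied grams could fall on escalation, so restoring post-rescue weights would not give total use. At 5% against 20%, a change of 50 to 100 g either way moves the difference by 0.15 × 50 = 7.5 to 0.15 × 100 = 15 g in either direction.
- **Diary data after IMP discontinuation are uncertain,** because Panel 3 and Section 14.3.10 conflict. The point rests on rescued subjects still on IMP, whose diary continues.

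**Conclusion.** The point holds for days without topical treatment. The specified model estimates a no-rescue quantity, while the endpoint runs from baseline to Week 16 and Week 26 and the diary captures topical rescue in subjects who remain on IMP. The size and direction of the gap cannot be determined from the documents. The illustrative shifts of 0 to 0.80 days a week rest on assumed rescue rates and an assumed equal loss per rescued subject in both arms, and other plausible inputs reverse the sign. It does not hold as an argument for changing the grams analysis. These are 'Other' endpoints outside the hierarchy in Section 14.3.6, so no primary or secondary conclusion changes. This is a worthwhile improvement, not a defect in the trial's main inference.

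**What to change.** 1. Add a treatment-policy analysis of days without topical treatment to Weeks 16 and 26, using all diary data regardless of rescue, and after IMP discontinuation where diary data exist. Continue to set aside data after COVID-19 subject-onset. The topical item starts at Week 0 and so has no baseline value; the existing mean model without a baseline term can be reused.
2. Keep the present exclusion model beside it, and state which of the two addresses the resource-use objective.
3. Reconcile Panel 3 footnote 5 with the statement in Section 14.3.10 about return of the eDiary, and the opening rule of Section 14.3.10 with its specific exclusion paragraph.
4. For grams, keep the current analysis and state that it covers supplied TCS only, because lower-potency products are not weighed and no weighing of rescue TCS is described.

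Cost: SAP wording, one dataset flag and one more analysis; no new data collection. The drawback is that diary data after IMP discontinuation may be sparse, so that part of the analysis should be reported with the number of subjects contributing.

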14.3.11 Analysis of exploratory supporting endpoints

There will be performed longitudinal analyses by visit/week of all primary, secondary and ‘Other’ efficacy endpoints, as specified in [Panel 4](#).

For the binary endpoints, the analyses will use the primary analysis of the primary estimand for each scheduled visit/week in the treatment period where an assessment is planned according to [Panel 2](#). The variables used for stratification (prior CSA use [yes/no] and baseline disease severity [IGA 3 or 4]) will be the same as the ones used for the primary analysis of the primary estimand.

For the continuous endpoints, a repeated measurements model using the same method described in the primary analysis of the primary estimand of the continuous secondary endpoints. The estimates and differences will be presented with 95% CIs, and nominal p-values for each scheduled visit/week in the treatment period where an assessment is planned according to [Panel 2](#).

14.3.12 Analysis of patient-reported outcomes

The PROs (POEM, DLQI, EQ-5D-5L [index and VAS scores], SF-36, and HADS) will be summarised by treatment group and visit using descriptive statistics based on the FAS.

The PROs collected in the eDiaries on a daily basis (Worst Daily Pruritus NRS, Eczema-related Sleep NRS) will all be summarised over time by treatment group using descriptive statistics based on the FAS.

To investigate a possible early onset of itch relief, a reduction in Worst Daily Pruritus NRS weekly average of at least 4 from baseline to Week 2 will be summarised by treatment group and analysed as described for the primary analysis of the primary estimand for the primary endpoint.

In the subgroup of subjects with either HADS-anxiety subscale score ≥ 8 or HADS-depression subscale score ≥ 8 at baseline, the proportion of subjects with both HADS-anxiety subscale score < 8 and HADS-depression subscale score < 8 at Weeks 16 and 26 will be summarised by treatment group and analysed as described for the primary analysis of the primary estimand for the primary endpoint.

The change from baseline to Weeks 16 and 26 in Eczema-related Sleep NRS weekly average, HADS, POEM, SF-36, and the EQ-5D-5L scores will be summarised by treatment group and domain, where applicable.

14.3.13 Analysis of safety

The analyses of safety will be based on the safety analysis set and the safety follow-up analysis set.

14.3.13.1 Adverse events

To assess the safety of tralokinumab in combination with TCS when used to treat severe AD for 26 weeks, the frequency of AEs and SAEs are included as additional secondary endpoints.

AEs will be coded during the course of the trial according to Medical Dictionary for Regulatory Activities (MedDRA). AEs will be presented by preferred terms (PTs) and primary system organ class (SOC).

Treatment-emergent AEs will be summarised, however, all AEs recorded during the course of the trial will be included in the subject data listings. An event will be considered treatment-emergent if started after the first use of IMP. The tabulations described in the following will only include the treatment-emergent events. In each of the tabulations, AEs will be defined by MedDRA PTs within primary SOC.

An overall summary of treatment-emergent AEs (the number of AEs, the number and percentage of subjects with an AE, and the event rate of AEs), deaths, SAEs, permanent discontinuations from the trial due to AEs, treatment-related AEs, and severe AEs will be presented.

The number of AEs and the number of subjects experiencing each type of AE will be tabulated by treatment group. The percentage of subjects with AEs will be compared between treatment groups by a chi-square test or Fisher's exact test (if expected cell count <5).

The severity for each type of AE will be tabulated by treatment group. The causal relationship to IMP and AxMP (TCS) for each type of AE will be tabulated by treatment group.

Related AEs are defined as AEs for which the investigator has not described the causal relationship to IMP as 'not related'. The number of related AEs and the number of subjects experiencing each type of related AE will be tabulated. The percentage of subjects with related AEs will be compared between treatment groups by a chi-square test or Fisher's exact test (if expected cell count <5).

SAEs and AESIs will be evaluated separately. A narrative for each SAE will be given. AESIs and AEs leading to withdrawal from trial or permanent discontinuation of IMP will be tabulated and listed.

Due to the COVID-19 pandemic and the implementation of home-use (self-injection) with telephone/video follow-up, overall safety monitoring could be impacted. To assess this, all AEs collected prior to and after the start of the COVID-19 pandemic will, in addition to being presented together, be presented separately for the overall summary of AEs and for all the AEs by SOC and PT.

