7.1 Overall trial design

Overview

This is a randomised, double-blind, placebo-controlled, parallel-group, multi-centre, phase 3 clinical trial in adult subjects with severe AD ineligible to treatment with CSA. The trial will consist of a screening period, a treatment period, and a safety follow-up period. The primary endpoint is assessed at Week 16, and the final efficacy assessment will be conducted at Week 26.

A schematic of the trial design is provided in [Panel 1](#).

Screening period (Week -6 to Week 0)

The screening period has a minimum duration of 2 weeks and a planned maximum duration of 6 weeks. The exact duration of the screening period for the individual subject depends on the length of any washout period needed (as also specified in the exclusion criteria in [Section 8.3](#)):

- 6 weeks for subjects using tanning beds or phototherapy.
- 4 weeks for subjects using systemic immunosuppressive/immunomodulating drugs, systemic corticosteroid use, or ≥ 3 bleach baths during any week within the 4 weeks.
- 2 weeks for subjects using topical PDE-4 inhibitors.

If no washout or a 2-week washout period is required, screening will be reduced to 2 weeks and reduced to 1 visit (Week -2; visit 2), i.e., the 2 planned screening visits will be merged. Eligibility will be assessed at the (first) screening visit and on Day 0 (hereinafter “baseline”) prior to randomisation.

All subjects will attend a screening visit 14 days before baseline (Week -2; visit 2) where they will receive electronic diary (eDiary) training and start completion of the electronic patient-reported outcome (ePRO) questionnaires in the eDiary. Data entered into the eDiary during the 2 weeks before randomisation will be used to calculate baseline values of the patient-reported outcomes (PROs).

All subjects will use an emollient twice daily (or more, as needed) for at least 14 days before randomisation and will continue this treatment throughout the trial (including safety follow-up). Subjects will initiate emollient treatment no later than the Week -2 visit. On lesional skin,

emollients should only be applied at a time where TCS is not applied; on TCS-untreated areas, the emollients may be applied at all times.

Treatment period (Week 0 to Week 26)

Following the screening period, approximately 250 subjects will be randomised 1:1 to one of the following groups stratified by prior CSA use (yes/no), country (Germany: yes/no), and baseline disease severity (IGA 3 or 4):

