14.3.5 Rescue treatment

Rescue treatment will be defined by the following algorithm:

Concomitant medications with ‘Dermatitis atopic’ or ‘Dermatitis infected’ as the preferred term (PT) for the indication, and either of the following:

- ATC2 code H02
- Preferred name Methotrexate, Methotrexate sodium, Ciclosporin, Azathioprine, Mycophenolate-mofetil, Mycophenolate-acid, Mycophenolate-sodium, Dupilumab, Crisaborole, or Alitretinoin
- ATC4 code D07AD or D07BD or D07CD or D07XD
- Confirmed rescue treatment (by investigator) in reported term for the indication, and ATC4 code D07AB or D07BB or D07CB or D07XB or D07AC or D07BC or D07CC or D07XC

As described in Section 9.5, investigators should make every attempt to conduct efficacy and safety assessments immediately before administering any rescue treatment. Therefore, if rescue treatment has start date the same day as an efficacy assessment, then it is assumed that the assessment is not influenced by rescue treatment.

Rescue treatment will be summarised for the entire treatment period as well as for the period up until the Week 16 visit (actual or nominal). Rescue treatment will also be summarised for the periods prior to and after the start of the COVID-19 pandemic, within the treatment period. The start date(s) of the COVID-19 pandemic will be decided prior to unblinding in the statistical analysis plan, possibly reflecting on when trial procedures were disrupted on a national level.

Additionally, rescue treatment will be summarised for the entire treatment period by the variables: prior CSA use (yes/no), country (Germany: yes/no), and baseline disease severity (IGA 3 or 4).

A summary table of rescue treatment by type (topical and systemic) and by overall group (corticosteroids, immunosuppressants, and other) will be made for the entire treatment period as well as for the period up until the Week 16 visit (actual or nominal).

[figure not shown]
In addition, the time to first use of rescue treatment will be presented using Kaplan-Meier plots for the whole treatment period.

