Appendix 8: Clinical Trial Protocol Addendum COVID-19

1 Rationale for clinical trial protocol addendum

The current COVID-19 pandemic warrants many subjects in the ECZTRA 7 trial to stay at home to comply with authority issued preventive measures. This make visits to the sites challenging, and in some cases impossible. To follow authorities restrictions and to safeguard the subjects in ECZTRA 7 as well as providing continued therapy to secure the scientific integrity, this clinical trial protocol addendum is installed to provide an opportunity for subjects to continue treatment with tralokinumab via home-use (self-injection).

No safety issues have been observed in subjects who applied home-use of IMP after training by site staff in previous or ongoing clinical trials with tralokinumab. Therefore, no safety issues are expected regarding home-use of IMP in ECZTRA 7.

2 GCP statement

Normal GCP procedures are followed for this protocol addendum. Subjects will be verbally informed and verbally consent to providing contact details (name, address, and telephone number) for shipping purposes.

3 eCRF recording

It must be recorded in the eCRF if the visit was conducted as a home-visit.

If the subject is reached by telephone/video contact and collection of AEs, concomitant medication and pregnancy test result (if applicable) are assessed, "Visit date" must be documented in the eCRF. All other assessments should be marked "Not done". The log line "If not done, specify reason" must be answered with "COVID-19". In addition, in the "Comments log", one log line per visit should be entered with "COVID-19" – as reason for only partly performed assessments at the visit.

If no contact can be established between site and subject at a given visit, this must be recorded as a missed visit in the eCRF ("Not done"). The log line "If not done, specify reason" must be answered with "COVID-19".

4 Description of visit scenarios

Without compromising the safety of subjects and site personnel, it is expected that efforts are made to secure attendance at sites for the Week 16 and Week 26 visits, securing important efficacy and safety assessments for the trial. Dependant on national guidelines regarding

COVID-19 and subject preferences, the remaining visits can follow three different scenarios as described below:

- 1) The subject is not restricted from attending visits at the clinic and continue to follow all procedures specified in the protocol.

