### Start of the COVID-19 pandemic

The start of the COVID-19 pandemic will be set to the 1st of March 2020 at time 00:00:00 across the whole trial. The date was decided based on the fact that at this date the trial procedures were most likely not impacted by the COVID-19 pandemic but still keeping it as close as possible to the first observed occurrence of missed procedures due to the COVID-19 pandemic.

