**Table 7: Start and end time of trial periods related to onset of the COVID-19 pandemic**

	Start of period	End of period (only if start date exists)
Treatment period, prior to the start of the COVID-19 pandemic	Exposure start if prior to the start of the COVID-19 pandemic else Missing	Whichever comes first of: Exposure end or Start of the COVID-19 pandemic
Treatment period, after the start of the COVID-19 pandemic	Start of the COVID-19 pandemic if between exposure start and exposure end else Exposure start if after the start of the COVID-19 pandemic else Missing	Exposure end if after the start of the COVID-19 pandemic else Missing
Safety follow-up period, prior to the start of the COVID-19 pandemic	Exposure end (plus 1 second) if prior to the start of the COVID-19 pandemic else Missing	Whichever comes first of: Date of safety follow-up visit (if existing) at time 23:59:59 else Date of last contact at time 23:59:59 or Start of the COVID-19 pandemic
Safety follow-up period, after the start of the COVID-19 pandemic	Start of the COVID-19 pandemic if between Exposure end (plus 1 second), and Date of safety follow-up visit (if existing) at time 23:59:59 else Date of last contact at time 23:59:59 else Missing	Date of safety follow-up visit (if existing) at time 23:59:59 else Date of last contact at time 23:59:59, if after the start of the COVID-19 pandemic else Missing

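### The AE split at 1 March 2020, meant to assess safety monitoring, takes no account of time on treatment

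*Protocol*

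**What the plan says.** Protocol 14.3.13.1 names two causes for concern, the pandemic itself and the "implementation of home-use (self-injection) with telephone/video follow-up, overall safety monitoring could be impacted". It gives the AE split the job of assessing that impact: "all AEs collected prior to and after the start of the COVID-19 pandemic will, in addition to being presented together, be presented separately". This applies to the overall summary and to AEs by SOC and PT. No test, threshold or decision rule is attached.

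SAP 6.8.2 sets the pandemic start to the 1st "of March 2020 at time 00:00:00 across the whole trial". Two reasons are given: "at this date the trial procedures were most likely not impacted by the COVID-19 pandemic", and the date should lie as close as possible to the first procedure missed because of the pandemic.

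SAP Table 7 divides each subject's treatment period at that date. For someone first dosed later, the after period begins at "Exposure start if after the start of the COVID-19 pandemic", so all of that subject's treatment time counts as after. SAP 6.7.1 keeps the treatment and safety follow-up periods apart.

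The overall summary in Protocol 14.3.13.1 includes an event rate. For the tables by type of AE, the text names only the number of AEs and the number and percentage of subjects. Neither document shows the split by time since first dose.

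**The concern.** The question is whether AEs were captured less well once visits were disrupted. A reader will look for a drop in AE reporting after 1 March 2020. For every subject on treatment at that date, however, before and after also mean earlier and later in treatment. If AEs are reported more often in the first weeks, a drop appears even when monitoring is unchanged. A real loss would look larger than it is. If the rate rose with time on treatment, a real loss could be hidden.

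The event rate in the overall summary does not cure this. It corrects for how much exposure each period holds, not for where in the 26 weeks that exposure falls. Showing the tables by arm does not cure it either: a loss of monitoring would affect both arms, so the inference rests on before against after.

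At stake is one descriptive safety assessment and the sentence about monitoring that the trial report would draw from it.

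**Working it through.** The plan gives no figure to reproduce here. The check is person-time algebra on the SAP Table 7 rule, then an illustration under stated assumptions.

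**1. Ordering (no assumption about AE rates).** Inputs: a 26-week treatment period (Protocol 7.1) and one cut date (SAP 6.8.2). For a subject randomised s weeks before the cut, 0 < s < 26, with full exposure:

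- before time runs from week 0 to s, mean s/2, below 13;
- after time runs from week s to 26, mean (s + 26)/2, above 13;
- difference: (s + 26)/2 - s/2 = 13 weeks, whatever s is.

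Subjects who finished before the cut average 13 weeks, all in the before period. Subjects randomised after it average 13 weeks, all in the after period. Pooled, the before mean is at most 13 and the after mean at least 13, strictly so if anyone straddles the date. Late-randomised subjects pull the after mean towards 13 but never below it. In one case run with discontinuation (0.5% per week in both periods), the order held: 11.5 against 15.6 weeks.

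**2. Size (assumptions; not in the documents).** Uniform randomisation between the dates shown, 182 treatment days each, identical ascertainment throughout. AE rate = r in Weeks 0-8, (1 + r)/2 in Weeks 8-16, 1 after Week 16. The ratio is the mean rate after divided by the mean rate before, each mean weighted by the exposure in each band.

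| Assumed enrolment | Weeks 0-8 share, before / after | r = 1.5 | r = 2 | r = 3 |
|---|---|---|---|---|
| 1 Dec 2018 - 31 Dec 2019 | 34% / 0% | 0.83 | 0.72 | 0.59 |
| 1 Mar 2019 - 31 Dec 2019 | 36% / 0% | 0.83 | 0.72 | 0.58 |
| 1 Dec 2018 - 29 Feb 2020 | 36% / 9% | 0.89 | 0.81 | 0.72 |
| 1 Mar 2019 - 29 Feb 2020 | 38% / 9% | 0.88 | 0.80 | 0.71 |
| 1 Dec 2018 - 15 Jun 2020 | 36% / 21% | 0.94 | 0.89 | 0.84 |

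Worked example, third row, r = 2. Exposure shares in the three bands are 0.093, 0.284, 0.623 after and 0.361, 0.314, 0.326 before. After: 0.093 x 2 + 0.284 x 1.5 + 0.623 x 1 = 1.235. Before: 0.361 x 2 + 0.314 x 1.5 + 0.326 x 1 = 1.519. Ratio 1.235 / 1.519 = 0.81.

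With r = 1 the ratio is 1.00 in every row.

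**3. Does banding repair it?** A smooth decline was also used: rate(t) = f + (1 - f) x 2^(-t/h), with h = 8 weeks and f = 0.5, or h = 4 weeks and f = 0.5 or 0.3. Enrolment started 30 to 60 weeks before the cut and ended between 13 weeks before and 30 weeks after it. With no loss of ascertainment:

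- crude ratio 0.69-0.91;
- within 2-week bins, weighted by total exposure per bin, 0.98-1.00;
- within the three bands 0-8, 8-16 and 16-26, weighted the same way, 0.91-0.99.

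With a true 20% loss (enrolment 60 weeks to 1 week before the cut, h = 4, f = 0.5), the crude ratio is 0.69, the 2-week ratio 0.79 and the three-band ratio about 0.77, against a true 0.80. Bands remove most of the distortion, and narrower bands remove nearly all of it.

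**The case against.** The strongest reply is that this is a descriptive supplement. AEs are also presented together, nothing is tested across the date, and within each calendar period the randomised arms have similar time on treatment. That stands, and it limits the importance of the point. It does not remove it, because the protocol says what the split is for.

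Second, the stated aim covers the pandemic as well as home-use, and for the pandemic a calendar split is the natural display. That stands, and the split should stay. Nor is the date itself open to complaint: it was set to keep the before period clean while lying close to the first disruption.

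Third, the size rests on a declining AE rate that appears in neither document. That stands. COVID-19 infections also count as ordinary AEs (Protocol 14.3.1) and would push the later rate up, which the illustration ignores and banding would not remove.

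A reader might go further in three ways that the documents do not support:

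- *After time is later for everyone, so AE rates must fall.* SAP Table 7 provides for subjects first dosed after the date, whose early weeks count as after. A fall needs a declining rate.
- *The rescue summary has the same flaw.* "Rescue treatment will also be summarised for the periods prior to and after the start of the COVID-19 pandemic", but Protocol 14.3.5 gives that summary no monitoring purpose and also plans Kaplan-Meier plots of time to first rescue.
- *Site against remote visits is the right contrast.* Appendix 8 says "It must be recorded in the eCRF if the visit was conducted as a home-visit", so a split may be possible. But mode depends on national guidelines and subject preference, so that contrast is itself confounded. It also leaves out visits with no contact, where capture is most at risk.

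**Conclusion.** The point holds as a limited, cheap improvement. The ordering of time on treatment follows from the cut rule under full exposure whenever a subject straddles the date. Whether it distorts the AE contrast depends on whether the AE rate changes with time on treatment, which the documents do not say. Under the assumed declines and enrolment dates in the table, the after/before ratio with unchanged monitoring is about 0.58-0.94; under a constant rate it is 1.00. As planned, the split cannot tell such a time trend from a loss of AE capture. Efficacy and the between-arm AE comparison are unaffected.

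**What to change.** In Protocol 14.3.13.1 and SAP 6.7.1:

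- Keep the calendar split as planned.
- Add AE event rates per patient-year before and after 1 March 2020 within time-on-treatment bands, for example Weeks 0-8, 8-16 and 16-26, by arm and pooled.
- State that any conclusion about monitoring rests on the within-band comparison.
- Optionally, add a split by recorded visit mode, labelled as descriptive support only.

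The cost is SAP wording and extra tables from dates already collected. The downside is small counts in some bands. A band may even be empty: if randomisation had ended on 31 December 2019, 61 days before the cut, no after time would fall in Weeks 0-8 (56 days). Such a band should be reported as not comparable. Wide bands leave some residual time trend, so narrower ones are preferable where counts allow.
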